#### 7. Postoperative pain control

In the postanesthetic recovery room (PACU), 30 mg ketorolac is administered intravenously as a rescue analgesic as a first-line rescue medication, followed by an additional 50 µg fentanyl (up to 2 doses).

In a general hospital room, tramadol 37.5 mg/acetaminophen 325 mg is administered orally three times from the time of drinking water. If bowel function has not yet recovered or pain cannot be controlled with oral medications, nalbuphine 10 mg, pethidine 25 mg, and tramadol 100 mg are administered intravenously in that order. If the patient has adverse reactions to narcotic analgesics, 100 mg of ketoprofen or 1 g of propacetamol are administered.

#### 8. Management of nausea and vomiting after surgery (PONV)

Ramosetron 0.3 mg is administered as a first-line antiemetic agent, and if vomiting / nausea persists, metoclopramide 10 mg and palonosetron 0.075 mg are administered.

#### 9. Postoperative urinary retention (POUR) management

Regardless of whether the patient feels a feeling of urination, if the bladder volume exceeds 600 ml, it is considered a urinary retention POUR. A separate doctor who did not participate in intraoperative anesthesia measures and calculates bladder volume using ultrasound with a Convex probe. Bladder volume is routinely assessed one hour after

arrival at the PACU, and if the patient feels urgency to urinate within one hour of arriving at the PACU, further evaluation of bladder volume is performed immediately. There are no additional costs for ultrasound examination.

The method of measuring the remaining amount of the bladder is as follows.

- After placing the ultrasonic probe on the upper part of the pubic bone, measure the widest width on the horizontal surface first, and measure the length on the longitudinal side. Finally, after measuring the depth from the front and rear sides, calculate the bladder volume with the formula (width x depth x length x coefficient (table below)).

Bladder Shape	Unknown	Triangular prism	Cylinder (Ellipsoid)	Cuboid	Spherical
Correction Coefficient	0.72 (most commonly used)	0.66	0.81	0.89	0.52

If urinary retention is identified, a Foley catheter is inserted into the patient. After placement of the Foley catheter, urine discharge is measured and bladder volume is reassessed. In principle, self-urination is not allowed, but in the case of autourination, the bladder volume is estimated by combining the amount of urination and the amount of residual urine.

#### 10. End-point timeline

The occurrence of urinary retention after surgery is measured at 1 hour, 24 hours, and 48 hours, respectively, based on the arrival time in the postoperative recovery room.

The first fart time is measured from the time you arrive in the recovery room after surgery.

Two days after surgery, chest X-ray imaging is performed to check for changes in radiological aeration such as pneumonia infiltration, lobe, segmental and segmental atelectasis.

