## 4. Research necessity and background

Post-COVID-19 conditions are a novel and poorly understood clinical disease with life-affecting ramifications, and recent studies have shown that patients have worsened their autonomic nervous system after COVID-19 and are potentially at risk of autonomic dysregulation/autonomic neuropathy.

Currently, most patients undergoing general anesthesia are using neuromuscular blockers, and the residual effect of neuromuscular block delays the recovery of autonomic functions of the body after surgery, and causes problems such as deterioration of bladder and bowel function after surgery. Therefore, reverse premise is used for postoperative muscle relaxation recovery, and clinically, sugammadex and neostigmine have been used a lot. Sugammadex generally provides rapid recovery, including recovery from muscle relaxation after surgery, compared to neostigmine, but postoperative outcomes have been reported with limited coverage in postoperative patients. Therefore, in this study, we

expect that sugammadex will help restore bowel function and lung function more than neostigmine after surgery in patients who have recovered from COVID-19 infection.

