After checking the TOF ratio  $\geq 0.9$ , the endotracheal tube is removed. If muscle relaxation recovery is delayed for more than 0 minutes, more than 2 mg / kg of sugammadex can be used regardless of the group, in which case the administration and dosage should be recorded separately.

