#### 15. Effectiveness evaluation items and methods

Study endpoints

Primary endpoints

Whether urinary retention occurs 1 hour after surgery

Secondary endpoints

Surgery time and anesthesia time

Recovery time after anesthesia

Intraoperative bleeding, vital signs

Whether and how to administer additional sugammadex

Bladder volume assessed at 1 hour postoperative (summing of autologous urination volumes)

Recovery score and pain score assessed at 1 hour after surgery

First fart time

Whether urinary retention occurs at 24 or 48 hours after surgery

Presence of acute lesions on chest x-ray 2 days after surgery

Actual use of pain and nausea control medications

Other intraoperative events (such as arousal (open eyes), involuntary movements, adverse events and unexpected side effects)

Independent variables

Patient gender, age, weight, height

American Academy of Anesthesiology Physical Classification (ASA class)

Heart rate, blood pressure, oxygen saturation (SpO2), muscle relaxation monitoring score (TOF)

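### The 1-hour retention endpoint and first flatus are timed from recovery-room arrival, which the randomised drug may shift, while section 15 counts the primary endpoint from surgery; one drug-independent time origin is needed

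*Combined protocol and SAP*

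**What the plan says.** Section 13, item 10, sets the clock. Retention is "measured at 1 hour, 24 hours, and 48 hours, respectively, based on the arrival time in the postoperative recovery room", and "The first fart time is measured from the time you arrive in the recovery room after surgery". Item 9 of the same section agrees: the routine bladder scan falls one hour after arrival, with an immediate extra scan "if the patient feels urgency to urinate within one hour of arriving at the PACU". The criterion there is a volume: "if the bladder volume exceeds 600 ml, it is considered a urinary retention POUR", whether or not the patient feels the need to void. Voiding is in principle not allowed before the scan, and any urine passed is added to the residual.

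Section 15 words the primary endpoint as "Whether urinary retention occurs 1 hour after surgery". It also describes the 1-hour bladder volume and the 1-hour recovery and pain scores as postoperative or after surgery. Section 22(2) likewise places the primary endpoint one hour after surgery. Section 15 lists "First fart time" with no start time, so the difference in wording concerns the 1-hour endpoints and not flatus.

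Under section 13, item 6, the blinded agent is given after surgery ends, once the TOF count has reached 2. Only after the TOF ratio reaches 0.9 is it that "the endotracheal tube is removed". Section 4 states the expected difference between the drugs: "Sugammadex generally provides rapid recovery, including recovery from muscle relaxation after surgery, compared to neostigmine".

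**The concern.** A time origin that follows randomisation and can depend on treatment does not give the two arms the same follow-up. If neostigmine patients take longer to reach the extubation criterion, they reach the recovery room later, and a scan one hour after arrival is then later relative to both surgery and study drug. Retention is defined by a volume threshold with voided urine added back, so the extra minutes can only add to the measured volume. Some difference in retention could then appear even if neither drug affects the bladder, and it would favour sugammadex.

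First flatus moves the other way. A later start to the clock removes the delay from the recorded time, which shortens neostigmine's result and works slightly against sugammadex.

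Separately, two origins are written for the primary endpoint. They differ by the interval from end of surgery to recovery-room arrival. No section fixes a common clock, bounds that interval or plans an adjustment for it.

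**Working it through.** **Sequence of events, from sections 13 and 4.** End of surgery → wait for TOF count 2 → blinded drug → TOF ratio 0.9 → extubation → recovery-room arrival → scan at arrival + 60 min. The wait for TOF count 2 comes before the drug and follows the same rule in both arms. Everything from the drug to arrival can depend on the arm. Hence:

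- Time from drug to scan = (drug to arrival) + 60 min. If neostigmine arrives d minutes later, its scan is d minutes later.
- Flatus time as recorded = (drug to flatus) − (drug to arrival). The same d is subtracted in the slower arm.

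**The plan's own figures (section 7).** The planning rates are 6/38 = 15.8% and 1/39 = 2.6%, a difference of 13.2 points. Exact two-sided Fisher power at 5% first reaches 90% at 101 per group (0.9021), and 101 × 1.1 = 111.1, rounded up to 112. This matches the stated 112 per group. The timing question does not change that number; 13.2 points is the yardstick below.

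**Size of the shift.** No input here is in the documents. Assumptions: d = 5 to 15 min; urine 60 to 180 ml/h (1 to 3 ml/min); no drug effect on the bladder; 1-hour volume normal with mean 350 ml and SD 200 or 150 ml in the faster arm.

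Extra volume = d × rate, from 5 × 1 = 5 ml to 15 × 3 = 45 ml.

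P(volume > 600) = 1 − Φ((600 − 350 − extra)/SD):

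| SD | Extra | z | P(>600 ml) | Spurious difference |
|---|---|---|---|---|
| 200 | 0 | 1.250 | 10.6% | – |
| 200 | 5 ml | 1.225 | 11.0% | 0.5 points |
| 200 | 45 ml | 1.025 | 15.3% | 4.7 points |
| 150 | 0 | 1.667 | 4.8% | – |
| 150 | 5 ml | 1.633 | 5.1% | 0.3 points |
| 150 | 45 ml | 1.367 | 8.6% | 3.8 points |

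The range is therefore about 0.3 to 5 points.

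**Cross-check anchored to the planning rates.** Set the faster arm's retention at 2.6% or 15.8%, with SD 150, 200 or 250 ml, urine 1 or 2 ml/min, 101 analysed per arm, a two-sided 5% test and a normal approximation.

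- Delay 5 or 10 min: retention rises by 0.1 to 3.4 points, by less than 1 point in 17 of the 24 combinations. The false-positive rate is 5.0% to 9.8%.
- Delay 20 or 30 min: retention rises by 0.5 to 11.5 points, and the false-positive rate is 5.6% to 51%.

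The result is sensitive to the baseline. With 15.8% in the faster arm and SD 150 ml, 45 ml moves z from 1.003 to 1.003 − 45/150 = 0.703, so retention becomes 24.1%, a rise of 8.3 points. That combines the longest delay, the highest urine rate, the smallest SD and the higher planning rate as the faster arm's baseline. The ranges illustrate and do not bound the effect.

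**The case against.** The strongest reply is that section 15 uses shorthand. Item 10 of section 13 itself speaks of retention after surgery and then defines the clock as recovery-room arrival, and item 9 agrees. This is probably right, but the primary endpoint still needs one origin stated everywhere.

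Second, the gap between arms is inferred. Section 4 gives no minutes, nothing says what besides extubation governs transfer, and item 6 allows extra sugammadex in either group when recovery is delayed, which limits the gap. This stands. A reader might infer that the arms are known to be scanned at different times; the documents support only that they may be.

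Third, every input to the magnitude is assumed. Normal(350, 200) even puts about 4% of bladders below zero volume, and the upper figures need the longest delay and highest urine rate together. This also stands: a short delay matters little.

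Fourth, retention one hour into the recovery-room stay is a coherent randomised outcome that includes whatever acts through slower emergence. That is fair. The shift is a bias only if the intended effect is on bladder function at a common time after surgery, which is how section 15 reads.

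Finally, a reader might infer that the trial could not tell a bladder effect from a clock shift. That is too strong: section 15 already collects surgery, anaesthesia and recovery times, so an arm difference in emergence could be seen. What is missing is a plan to record the drug-to-scan interval and use it.

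**Conclusion.** The point holds in a limited form. The primary endpoint has two written origins, and the operative one, recovery-room arrival, follows the randomised drug and may come later with neostigmine. The direction is clear if that delay exists: slightly in favour of sugammadex on retention and 1-hour bladder volume, slightly against it on first flatus.

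Under the main assumptions the spurious retention difference is roughly 0.3 to 5 points against the planned 13.2. Short delays mostly give less than 1 point; larger distortions need long delays or a high baseline rate. It should not be read as explaining the planned difference. The flatus effect is the same 5 to 15 minutes and is likely minor if that outcome runs to hours; the effect on retention at 24 and 48 hours should also be small.

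Confidence is high on the wording and the order of events, and low on the size. The correction is worth making because it is cheap and because, if the interval goes unrecorded, the alternative explanation is hard to examine afterwards.

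**What to change.** 1. Reconcile section 13 (items 9 and 10), section 15 and section 22(2) to one stated origin for endpoint measurement that the drug cannot move. End of surgery, defined as a recorded event, already matches sections 15 and 22(2). The recorded time of the blinded reversal agent would serve equally, and noting it reveals nothing because both agents are prepared as the same 5 cc volume. State a window around the 1-hour assessment, and compute first flatus from the same origin.
2. Record the drug-to-recovery-room and drug-to-scan intervals and report them by arm.
3. Add to section 16 a sensitivity analysis of the primary endpoint and the 1-hour bladder volume adjusted for the drug-to-scan interval. State that this interval is itself post-randomisation, so the analysis is supportive and does not replace the unadjusted comparison.
4. Leave the urgency-scan and catheterisation rules in item 9 to the investigators. Those passages need only be made consistent with the chosen endpoint clock.

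Cost: an amendment to wording, one extra recorded time and a little more analysis. The endpoint scan may fall somewhat earlier in the recovery-room stay. No patient or procedure is added.

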#### 14. Standard treatment method for target disease

The anaesthesia method used in this review is the standard of care currently common in all patients undergoing general anaesthesia, and this review does not change the anaesthesia method or other medical interventions.

#### 15. Effectiveness evaluation items and methods

Study endpoints

Primary endpoints

Whether urinary retention occurs 1 hour after surgery

Secondary endpoints

Surgery time and anesthesia time

Recovery time after anesthesia

Intraoperative bleeding, vital signs

Whether and how to administer additional sugammadex

Bladder volume assessed at 1 hour postoperative (summing of autologous urination volumes)

Recovery score and pain score assessed at 1 hour after surgery

First fart time

Whether urinary retention occurs at 24 or 48 hours after surgery

Presence of acute lesions on chest x-ray 2 days after surgery

Actual use of pain and nausea control medications

Other intraoperative events (such as arousal (open eyes), involuntary movements, adverse events and unexpected side effects)

Independent variables

Patient gender, age, weight, height

American Academy of Anesthesiology Physical Classification (ASA class)

Heart rate, blood pressure, oxygen saturation (SpO2), muscle relaxation monitoring score (TOF)

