## **13. Study design and methods**

1. This study is conducted in patients scheduled for surgery under general anesthesia in a

single-organ, randomized, parallel design, and double-blinded.

Study subjects who have completed screening tests and voluntarily agreed to participate in this study among subjects who meet the inclusion/exclusion criteria will be randomized 1:1 to the Sugammadex injection group or the neostigmine injection group (control). The assignment of the two groups is randomized by computer-generated randomization method by a table using [www.randomization.com](http://www.randomization.com). The expected research flow chart is as follows.

2. After the patient enters the operating room, the patient is equipped with an electrocardiogram, oxygen saturation, esophageal thermometer, electroencephalography, non-invasive blood pressure monitoring device, and muscle relaxation monitoring equipment (TOF equipment). The method of anesthesia is according to the standard anesthesia method and is described in detail below.

3. Preanesthetic treatment: Midazolam 2 mg

4. Anesthesia inducer: Anterior venous anesthesia (propofol 2~1.5 mg/kg)

5. Neuromuscular blockers: Rocuronium 0.6 mg/kg IV in tracheal intubation , additional administration of rocuronium to keep TOF below 2 during surgery, 0.15 mg/kg.

6. Neuromuscular reversal: TOF results are checked at the end of surgery and neostigmine or sugammadex is administered according to the instructions. If TOF < 2, postpone administration until TOF 2 or higher spontaneously recovers. When recovering from TOF 2 or more, a prepared neuromuscular reversal agent is administered.

Neostigmine 50µg/kg + glycopyrrolate 0.01mg/kg in the Neostigmine group

Sugammadex 2mg/kg from Sugammadex group

Neuromuscular reversal is received and prepared in advance by a separate medical staff (a separate anesthesiologist who does not participate in the patient's anaesthesia) using the drug and the corresponding prescription order is made separately at the time of leaving the patient recovery room. Since it is diluted with saline and prepared in a total of 5 cc, the patient and the patient's anesthesiologist will not know the drug until they leave the recovery room (double-blinded).

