## 16. Statistical analysis method

Statistical analysis will be performed using SPSS software. (SPSS version 22.0, IBM Corporation, Armonk, NY, USA),

Continuous variables (variables expressed as mean  $\pm$  standard deviations) will be compared using an independent t-test or Mann-Whitney U test, and categorical variables (including the presence of urinary retention and other adverse events) will be compared using a chi-squared test (or Fisher's exact test). Data are expressed as mean  $\pm$  standard deviation, median (25; 75 median), or number of patients (%). If the p-value is less than 0.05, it is considered to have statistical significance.

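### Surgery time and intraoperative bleeding are listed as secondary effectiveness endpoints, although both are complete before the randomised reversal agent is given

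*Combined protocol and SAP*

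**What the plan says.** **Section 15** (effectiveness evaluation) names urinary retention at 1 hour as the primary endpoint. The secondary endpoints include:

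- "Surgery time and anesthesia time"
- "Intraoperative bleeding, vital signs"
- "Other intraoperative events (such as arousal (open eyes), involuntary movements, adverse events and unexpected side effects"

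The same section has a separate list of independent variables: patient characteristics, ASA class, heart rate, blood pressure, SpO2 and TOF.

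**Section 13**, item 6, fixes the time of dosing: "TOF results are checked at the end of surgery and neostigmine or sugammadex is administered according to the instructions". Dosing can be later still: "If TOF < 2, postpone administration until TOF 2 or higher spontaneously recovers". The tube is removed after a TOF ratio of at least 0.9 has been confirmed.

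**Section 14** says that "this review does not change the anaesthesia method or other medical interventions".

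**Section 16** says that continuous variables "will be compared using an independent t-test or Mann-Whitney U test" and that categorical variables get a chi-squared or Fisher's exact test. It then sets one threshold: "If the p-value is less than 0.05, it is considered to have statistical significance". It has no descriptive-only class of variable and no multiplicity rule.

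**The concern.** An effectiveness endpoint has to be something the randomised treatment could alter. Here the arms differ only in the reversal agent, which is given once the operation is over. Surgery time and blood loss during surgery are fixed by that point.

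If they are tested and reported among the effectiveness results, a chance p-value below 0.05 would sit beside real outcomes and could be misread as shorter operations or less bleeding with one drug. The same two variables are useful in another role: described by arm, they show whether the operations in the two groups were comparable.

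**Working it through.** **Order of events.** The question turns on timing, so the passages are set in sequence.

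1. Anaesthesia and surgery follow the same method in both arms (sections 13 and 14). The anaesthesiologist is blinded until the patient leaves the recovery room (section 13), so knowledge of the arm should not affect how the operation is run.
2. Surgery ends and TOF is checked. If it is below 2, dosing waits (section 13).
3. The randomised agent is given.
4. A TOF ratio of at least 0.9 is confirmed and the tube is removed.
5. Recovery room; primary endpoint at 1 hour.

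**Where each listed item falls.**

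| Section 15 item | Position relative to dosing |
|---|---|
| Surgery time | Complete by step 2: before |
| Intraoperative bleeding | Complete by step 2: before |
| Anesthesia time | Can run through step 4: may respond to the drug |
| Vital signs | No window stated: may include readings between steps 3 and 4 |
| Other intraoperative events | No window stated: arousal or movement during surgery is before; adverse events recorded up to extubation may be after |

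Only surgery time and intraoperative bleeding are securely before dosing.

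**Chance of a spurious result.** The plan gives no figure for this. Inputs: a per-test threshold of 0.05 (section 16); two variables for which the null is true by design; one test each (an assumption, since the plan does not say how many tests an item generates).

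- One test: 0.05, or 5%.
- At least one of two, independent: 1 − 0.95² = 1 − 0.9025 = 0.0975, or 9.75%.
- Upper bound whatever the dependence: 2 × 0.05 = 0.10, or 10%.
- Perfectly dependent tests: 5%.

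If longer operations tend to bleed more, the figure lies between 5% and 9.75%.

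**Sample size.** Section 7 builds its 112 per group on dysuria frequencies of 6/38 and 1/39. None of the variables discussed here enters that calculation, so reclassifying them leaves it unchanged.

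**The case against.** The strongest reply is that section 16 is a generic paragraph. It names no test for surgery time or bleeding and nowhere says that a difference in either would be credited to a drug. Anaesthesia trials routinely record both, and the authors may have meant only to tabulate them. This stands in part: testing is inferred from a general rule. But the rule exempts nothing, and section 15 has a separate list for patient characteristics that does not contain these two items. As written, they are outcomes.

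Four stronger readings are tempting, and the documents do not support them.

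- *All four groups of variables (surgery time, bleeding, vital signs, events) precede dosing.* The word intraoperative may govern only bleeding in that line. Vital signs and events have no stated window, and the interval between reversal and extubation follows the drug. A real drug effect there is possible.
- *The false-positive risk is 19% or 26%.* These are 1 − 0.95⁴ = 0.185 and 1 − 0.95⁶ = 0.265. They count vital signs and events as certain nulls, which is not shown, and they assume independence.
- *Vital signs serve as both outcome and predictor.* They do appear in both lists, but section 16 plans no model or adjustment that uses the independent variables, so the overlap has no analytic consequence.
- *The plan would present a difference as an effect of sugammadex.* No sentence says so. It is a reading of the section heading together with the general threshold.

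**Conclusion.** The point holds for surgery time and intraoperative bleeding. They are misclassified as effectiveness endpoints, because both are complete before the randomised agent is given. A significant difference in either would be a chance imbalance with probability 5% per test, and 9.75% for at least one of the two under independence.

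This assumes that randomisation and blinding are intact, that surgery time stops at the end of the operation (the protocol does not define it), and that each item is tested once under the general rule. If randomisation or blinding failed, a difference could have another cause, but it would still not be an effect of the drug.

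For vital signs and other intraoperative events, the documents support only the narrower statement that the measurement window is undefined. Anesthesia time shares a line with surgery time but is a legitimate outcome.

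The consequence is small. These are secondary endpoints, and the primary endpoint, its test and the sample size are unaffected.

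**What to change.** 1. In section 15, move surgery time and intraoperative bleeding from the secondary endpoints to a list of operative characteristics. State in section 16 that these are summarised by arm without a significance test.
2. For vital signs and other intraoperative events, split the record at the time of reversal. Describe values and events before it; keep only those after it as outcomes.
3. Give anesthesia time its own line and keep it as an outcome.

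The cost is a few lines of text in sections 15 and 16, best made before the groups are compared. No patients, visits or measurements are added.
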